### **8.2 Premature Study Discontinuation**

- Request by the participant to withdraw.
- Request of the primary care provider if s/he thinks the study is no longer in the best interest of the participant.
- Participant judged by the investigator to be at significant risk of causing harm to self.
- At the discretion of the IRB, Food and Drug Administration (FDA), Office for Protection of Human Research Participants, investigator, or the sponsor.

### **8.3 Early Discontinuation**

Any participant who develops a Grade 3 or 4 symptom or laboratory abnormality (other than bilirubin, cholesterol and triglycerides, UNLESS THE INVESTIGATOR HAS A COMPELLING REASON TO THINK IT IS NOT RELATED TO STUDY DRUG) will be evaluated and will have study treatment withheld until the toxicity resolves ( $\leq$  Grade 2). If the abnormality is thought to be related to study treatment, the participant will not be rechallenged without discussion with [name] (see Section 7.2). Participants who have to discontinue study drug early (for the above listed reasons or confirmed virologic failure) but have been on study drug for at least 12 weeks will undergo a final safety evaluation, blood draw for stored serum and plasma, DXA scan and FibroScan. All participants will remain in follow-up for resolution of Grade 3 or 4 toxicities.

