### **5.4 Concomitant Medications**

#### Prohibited Medications

The prohibited medications are:

Anticonvulsants: Phenobarbital, Phenytoin, Carbamazepine, Oxcarbazepine

Antimycobacterial: Rifampin, rifapentine

Herbal Products: St. John's wort, Echinacea

Antiarrhythmic Agents: Dofetilide

GI Motility Agents: Cisapride

ART: Atazanavir

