### **7.2 Grade 3 Toxicity**

Participants who develop a Grade 3 AE or toxicity should have all antiretroviral medications, including study drug, withheld unless the investigator has compelling evidence that the AE has NOT been caused by the study drug. The study chair ([name]) should be notified of any Grade 3 or greater toxicity. The subject should be re-evaluated closely until the AE returns to Grade  $\leq 2$ , at which time study drug may be reintroduced at the discretion of [name] or according to standard practice.

If the same Grade 3 AE recurs within 4 weeks following reintroduction and it is thought to be related possibly, probably, or definitely to study drug, then study drug must be permanently discontinued. If the same Grade 3 AE recurs after 4 weeks but is not believed to be related to study drug, the management scheme outlined above may be repeated.

Participants experiencing Grade 3 or greater AEs (requiring permanent discontinuation of study drug) should be followed closely for resolution of the AE to Grade  $\leq 2$ , and [name] must be consulted.

Participants with Grade 3 asymptomatic laboratory abnormalities in cholesterol, triglycerides or bilirubin (if on atazanavir) may continue study drug.

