### **7.3 Grade 4 Toxicity**

Participants who develop a Grade 4 symptomatic AE or toxicity will have study drug discontinued. If the site investigator has compelling evidence that the AE has not been caused by the study drug, dosing may resume when the AE has resolved and after consulting [name]. Participants experiencing Grade 4 AEs requiring permanent discontinuation of study drug should be followed closely until resolution of the AE to Grade  $\leq 2$ , and [name] must be consulted.

Participants with Grade 4 asymptomatic laboratory abnormalities in cholesterol or triglycerides may continue study drug.

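### Sections 7.2, 7.3 and 8.3 conflict on bilirubin and on restarting study drug after a related Grade 4 event, so the discontinuation part of the primary endpoint has no single rule behind it.

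*Combined protocol and SAP*

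**What the plan says.** Section 7.2 (Grade 3): participants "should have all antiretroviral medications, including study drug, withheld unless the investigator has compelling evidence" that study drug was not the cause. It then makes an exception: "Participants with Grade 3 asymptomatic laboratory abnormalities in cholesterol, triglycerides or bilirubin (if on atazanavir) may continue study drug". Atazanavir is an exclusion under Section 4.2.1 and appears among the prohibited drugs in Section 5.4 as "ART: Atazanavir".

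Section 7.3 (Grade 4): "Participants who develop a Grade 4 symptomatic AE or toxicity will have study drug discontinued". Dosing may restart after resolution and consultation if there is compelling evidence that the drug was not the cause. The exception is: "Participants with Grade 4 asymptomatic laboratory abnormalities in cholesterol or triglycerides may continue study drug". Bilirubin is not listed.

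Section 8.3 (Grade 3 or 4): drug is held until the event falls to Grade 2 or lower, for abnormalities "other than bilirubin, cholesterol and triglycerides". A capitalised UNLESS clause about relatedness sits inside the same bracket. An event thought to be related may not be rechallenged without prior discussion, and the reader is pointed back to 7.2.

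Section 8.1 lists drug-related toxicity that requires permanent discontinuation and refers to Section 7.1 for it. Section 7.1 covers Grades 1 and 2 and lets study drug continue.

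Section 9.3 makes stopping of study drug for related adverse events one component of the primary endpoint. Related laboratory or clinical events of Grade 3 or higher are another, counted regardless of whether drug was stopped.

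**The concern.** An endpoint that counts discontinuations is only as well defined as the rules that produce them. If two sections give different instructions for the same event, the count depends in part on which page was consulted. Total bilirubin is a scheduled safety laboratory test (Sections 6.1 and 6.6), so the bilirubin conflict concerns something measured routinely.

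Two further features raise the stakes. Section 7.0 mandates the toxicity rules only for Arm A, so the ambiguity falls on one side of the comparison. Section 9.6.1 also ends a participant's contribution to the primary outcome once drug has been stopped for 14 or more consecutive days, so the choice of rule can remove later HIV-1 RNA results from the as-treated analysis. For bilirubin, whether a participant stays on drug during the abnormality also depends on the section followed, which is a safety matter in its own right.

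**Working it through.** No figure in the plan rests on these rules, so the main check is to apply each section to the same drug-related event.

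| Related event | 7.2 | 7.3 | 8.3 |
|---|---|---|---|
| Grade 3 bilirubin | Hold; the exception needs atazanavir | Not applicable | Outside the hold rule |
| Grade 4 bilirubin | Not applicable | No exception listed | Outside the hold rule |
| Symptomatic Grade 4 event | Not applicable | Discontinue; restart described only if compelling evidence shows the drug was not the cause | Hold to Grade 2 or lower; rechallenge possible after discussion |

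**Row 1.** The exception "bilirubin (if on atazanavir) may continue study drug" requires a drug that 4.2.1 and 5.4 rule out. In Arm A the study regimen also replaces the entry regimen (5.1). No compliant participant can meet the condition, so 7.2 in effect always holds drug for a related Grade 3 bilirubin event, while 8.3 does not.

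**Row 2.** The conflict is clearest when the abnormality is symptomatic or is treated as a toxicity under 7.3. For an asymptomatic non-lipid Grade 4 laboratory value, 7.3 gives no explicit instruction.

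**The UNLESS clause.** It can be read as limiting the hold rule or as limiting the exemption. Either way it concerns events thought unrelated to study drug. For a related bilirubin event the mismatch with 7.2 and 7.3 remains on both readings.

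**Row 3.** Both sections stop drug at onset. They differ on whether a related event may lead to a restart.

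**Link to the endpoint.** In each row the discontinuation count for that participant can be 0 or 1. A hold is not automatically a discontinuation. However, 8.1 lists a stop of 14 or more consecutive days as a reason for permanent discontinuation, and the protocol does not say whether a hold it mandates itself counts towards that.

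**Size.** Inputs from Section 9.1: 24 enrolled per arm, 20 per arm in the power statement. Shift in the Arm A discontinuation rate = k/n for k reclassified participants.

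- n = 24: 1/24 = 4.2 points; 3/24 = 12.5 points.
- n = 20: 1/20 = 5.0 points; 3/20 = 15.0 points.
- Exact (Clopper-Pearson) 95% intervals: 0/24 gives 0 to 14.2%, 1/24 gives 0.1 to 21.1%; 0/20 gives 0 to 16.8%, 1/20 gives 0.1 to 24.9%.

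The documents give no expected rate for these events. The range of 1 to 3 affected participants is an assumption for illustration.

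**The case against.** The strongest reply is that little of the primary endpoint can move. Section 9.3 counts related Grade 3 or higher events whether drug is stopped or not, so every related event in the table enters the tolerability result under any of the sections. This stands. A reader might infer that the primary endpoint as a whole depends on the section followed; the documents do not support that.

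Second, the Grade 4 contrast should not be overdrawn. Section 7.3 does not explicitly forbid restarting after a related event; it describes a restart only for the other case. Its use of discontinued is not always permanent, since it allows resumption and refers separately to permanent discontinuation. Section 8.3 restricts rechallenge rather than granting it. A reader might infer that exposure during a symptomatic Grade 4 toxicity differs between the sections, but both stop drug. The difference is confined to restart, and if a hold of 14 or more days triggers 8.1 and 9.6.1, the two routes may converge.

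Third, two omissions might be taken for further contradictions. Section 7.3 gives no explicit instruction for asymptomatic non-lipid Grade 4 laboratory values, but 8.3 covers them (bilirubin aside). Section 7.2's recurrence rule addresses the case "If the same Grade 3 AE recurs after 4 weeks but is not believed to be related to study drug" and says nothing of a related event that recurs that late, but its general Grade 3 rule and 8.3 largely cover it. These are gaps in layout, not conflicting instructions.

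Fourth, a reader might call 8.3's bilirubin exemption unconditional. The UNLESS clause makes that unsafe; what can be said is that it carries no atazanavir condition.

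Finally, Grade 3 or higher toxicities go to the study chair, restart decisions run through a named role, and the documents name a single clinic. This reduces inconsistency between decision-makers. It does not supply a prespecified rule, and in an open-label trial case-by-case decisions are made with the arm known.

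**Conclusion.** The protocol contradicts itself on bilirubin at Grades 3 and 4 and on restart after a related symptomatic Grade 4 event, and 8.1 refers to the wrong section for toxicity requiring permanent discontinuation. For first-occurrence Grade 3 events other than bilirubin, 7.2 and 8.3 broadly agree.

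The statistical consequence is narrow: the discontinuation component in 9.3, and as-treated follow-up under 9.6.1 when a stop reaches 14 days. Each reclassified Arm A participant is worth 4.2 points with 24 in the arm. That figure would hold for any single event in an arm of this size and does not show that any participant will be affected. The trial is a pilot with exploratory analyses, which also limits the weight of the point. It still deserves correction, because the instructions bear on participant safety and on a primary endpoint component.

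**What to change.** The sponsor's clinical team should reconcile Sections 7.2, 7.3, 8.1 and 8.3 so that each grade and type of event has one instruction. A single table by grade, by symptomatic or laboratory event, and by analyte would do this. The reconciliation should settle bilirubin at Grades 3 and 4 in light of the atazanavir prohibition, make the scope of the UNLESS clause explicit, state the restart position after a related Grade 4 event, and correct the cross-reference in 8.1. The same table can state the two cases now left implicit: asymptomatic non-lipid Grade 4 laboratory values and late related recurrence. Which action belongs in each cell is a clinical decision, and none is proposed here.

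Section 9.3 should state whether discontinuation means a temporary hold or a permanent stop, and Section 9.6.1 whether a protocol-mandated hold counts towards the 14 days. The cost is protocol wording: no added visits, participants or measurements.

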## **9.0 Sample Size and Endpoints**

### **9.1 Sample size**

Since a high percentage of participants are expected to have hepatic steatosis, we will base the sample size around the desired effect size for FibroScan CAP measurement. The sample size for this project is derived

from studies of CAP in HIV-infected but non-TW populations. Using a median baseline CAP of 237 dB/m (standard deviation [SD] 53), 20 TW per arm provides 90% power to detect a minimum between-group CAP difference of 56 dB/m, which is clinically significant. We will enroll 24 TW per arm to allow for up to 20% discontinuation or loss-to-follow-up, which is reasonable for this high-risk population. Therefore, the total sample size will be 48 participants.

Additionally, perturbations of inflammatory, metabolic and coagulation pathways by exogenous female hormone use and the intersections of these perturbations with those associated with HIV are unknown. Therefore, it should not be assumed that the effects of switching ART to bictegravir + emtricitabine + tenofovir alafenamide on immunometabolic biomarkers in transwomen will be similar to those observed with integrase inhibitor or tenofovir alafenamide use in other HIV-infected populations. As such, we will assess the effects of switching ART to bictegravir + emtricitabine + tenofovir alafenamide vs continued ART on multiple biomarkers, including soluble CD14 (sCD14), a monocyte activation and mortality-associated biomarker that has been previously been shown by us and others to decline following switch to an integrase inhibitor. If similar declines in sCD14 and variability are observed following switch to bictegravir + emtricitabine + tenofovir alafenamide, 48 participants will provide >99% power to observe this clinically significant effects.

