## 6.0 Clinical Evaluations

### 6.1 Schedule of Events

	Screen	Baseline*	Week 4	Week 12	Week 24*	Week 36	Week 48*	Early Discontinuation
Demographics	X							
Hormone therapy questionnaires		X						
Medical and medication history	X							
Targeted physical exam with weight, vital signs		X	X	X	X	X	X	
Complete physical exam and height	X							
DXA for bone mineral density, lean and fat mass		X					X	X
FibroScan for hepatic steatosis and fibrosis assessment		X					X	X
HIV-1 RNA	X		X	X	X		X	X
Safety labs**	X	X	X	X			X	X
CD4 + T lymphocyte count		X		X	X		X	X
Fasting lipids, banked serum and plasma samples for insulin and biomarkers		X			X		X	X
Medication dispensation		X	X	X	X	X		

\* Entry, week 24 and week 48 laboratory evaluations are required to be fasting (at least 8 hours)

\*\*Safety labs include: CBC with differential, chemistry panel including liver enzymes (ALT, AST, Alk Phos), total bilirubin and serum creatinine. All safety labs, HIV-1 RNA, and CD4+ T lymphocyte counts will be performed at local certified laboratories.

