## 6.4 Discontinuation Evaluations

### Evaluations for Randomized or Registered Participants Who Do Not Start Study Treatment

Participants who do not start study treatment will be taken off study with no further evaluations required. The subject will be replaced. All case report forms (CRFs) must be completed and keyed for the period up to and including week 0.

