### Premature Study Treatment/Background ART Discontinuation Evaluations

Participants who discontinue study drug due to an AE will be followed on-study off drug. The subject will complete all study evaluations and then be taken off study.

Participants who discontinue study drug for  $\geq 14$  days or who have confirmed virologic failure (two measurements  $> 200$  copies/mL) will complete the Discontinuation Visit evaluations and then be taken off study.

Similarly, participants randomized to Arm B who discontinue their entry ART regimen for  $\geq 14$  consecutive days will complete the Discontinuation Visit evaluations will and then be taken off study.

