## **9.6 Analyses**

A descriptive analysis of demographic and clinical characteristics will be generated. Continuous variables will be expressed as mean  $\pm$  SD if normally distributed or median with IQR if not normally distributed. Data will be pooled by arm and stratified by ART 3rd drug class. CAP will be used continuously and categorically, using for the latter the following standardized steatosis cut-offs: Grade 1 238 dB/m, Grade 2 260 dB/m and Grade 3 292 dB/m. DXA data will be used continuously for lean and fat mass measurements, and, for bone mineral density, both continuously and categorically, with the latter using standard cutoffs for osteopenia and osteoporosis. Biomarker levels may be log-transformed, where appropriate. Wilcoxon rank-sum and Pearson  $\chi^2$  tests will compare continuous and categorical variables, respectively, between and within groups. Although the sample size is small, regression modeling will be attempted to assess if any observed differences persist after adjustment for confounding factors. All statistical tests will be 2-sided ( $\alpha=0.05$ ). Analysis will be exploratory without adjusting for multiple testing. [name] and [name] (statistician) will oversee analysis plan development/implementation.

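### Does enrolling 24 per arm fall short of the 20% loss allowance in section 9.1?

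*Combined protocol and SAP*

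**What the plan says.** Section 9.1 sizes the trial on the FibroScan CAP measurement, with an SD of 53 dB/m taken from a published cohort of people with HIV who were not transwomen. It states that "20 TW per arm provides 90% power to detect a minimum between-group CAP difference of 56 dB/m". It then adds the allowance for loss: "We will enroll 24 TW per arm to allow for up to 20% discontinuation or loss-to-follow-up". The total is 48.

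Section 9.1 does not name the test behind the 90%. Section 9.6 sets two-sided testing at 0.05 and names the tests for continuous and categorical variables ("Wilcoxon rank-sum and Pearson" χ²). It calls the analysis exploratory. CAP is listed among the secondary endpoints in section 9.4.

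Other sections bear on how many participants will lack a later CAP value:

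- Section 6.4, on participants who never start study treatment: "The subject will be replaced".
- Section 6.4, on those who stop study drug for an adverse event: "The subject will complete all study evaluations and then be taken off study".
- Section 6.1 marks the row "FibroScan for hepatic steatosis and fibrosis assessment" at baseline, week 48 and early discontinuation.
- Section 8.3 gives those who stop early after at least 12 weeks on drug a "final safety evaluation, blood draw for stored serum and plasma, DXA scan and FibroScan".

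**The concern.** The figure 24 equals 20 × 1.2. That adds 20% to the evaluable number, whereas allowing for a 20% loss means removing 20% from the enrolled number. The two calculations are often confused, and the first always gives the smaller answer. Here it gives 24 where 20/0.8 gives 25. If 20% really were lost, the arms would average 19.2, below the 20 on which the 90% rests.

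The second worry is that the 90% has no test attached. If it came from a t-test while the analysis uses ranks, the planned analysis could have less power than stated even with no loss beyond the allowance.

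At stake would be a trial slightly underpowered for the endpoint that set its size, and a protocol that claims more tolerance of dropout than it has.

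**Working it through.** **Inputs.** Difference 56 dB/m, SD 53, 20 evaluable per arm, 90% power, 24 enrolled per arm, loss up to 20% (all section 9.1). Two-sided 0.05 and rank-sum test (section 9.6). Equal allocation (section 9.2).

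**1. Reproduce the stated power.** Standardised difference d = 56/53 = 1.057. For a two-sample t-test with arms n₁ and n₂, the noncentrality is d × √(n₁n₂/(n₁+n₂)), with n₁+n₂−2 degrees of freedom.

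- 20 and 20: 1.057 × √10 = 3.34, 38 df, power 90.2%. The difference detectable with 90% power is 55.8 dB/m, which rounds to 56.

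The plan's figure is therefore reproduced by a two-sided two-sample t-test at 0.05. That this was the method used is an inference, since section 9.1 does not say so.

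**2. The loss allowance, three readings.**

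| Reading of 20% | Calculation | Evaluable |
|---|---|---|
| Ceiling within each arm | 0.20 × 24 = 4.8, so at most 4 lost (4/24 = 16.7%; 5/24 = 20.8% exceeds 20%) | 20 per arm |
| Ceiling pooled over the trial | 0.20 × 48 = 9.6, so at most 9 lost (9/48 = 18.75%) | 39 in total |
| Expected rate | 24 × 0.8 | 19.2 per arm on average |

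On the first reading the sentence in section 9.1 is true. On the second the trial is one participant short of 40. On the third it is 0.8 of a participant short per arm.

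**3. What the shortfall costs (t-test, 56 dB/m, SD 53).**

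- 20 and 19: noncentrality 3.30, 37 df, power 89.5%.
- 19 and 19: noncentrality 3.26, 36 df, power 88.7%. The difference detectable with 90% power is 57.3 dB/m.

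The largest fall is 90.2 − 88.7 = 1.5 percentage points.

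**4. Would 25 per arm secure 20?** Assume each participant independently has a 20% risk of no later CAP value. The documents do not give this; it is for illustration only.

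- 24 enrolled: P(at most 4 lost) = 0.460 in one arm; both arms 0.460² = 0.21. Average t-test power 88.6%.
- 25 enrolled: P(at most 5 lost) = 0.617 in one arm; both arms 0.617² = 0.38. Average t-test power 89.9%.

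The extra participant per arm buys 89.9 − 88.6 = 1.3 points. Even with 25, both arms keep 20 less than half the time, because any fixed allowance is subject to chance.

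**5. The rank-sum test.** Simulation with normal data, SD 53 and a shift of 56 gives about 88.5% at 20 and 20, and 86% to 87% at 19 and 19. The gap from the t-test at 20 per arm is 90.2 − 88.5 = 1.7 points. It depends on the assumed normal shape, which the documents do not establish for CAP.

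**The case for a change.** The case for a correction is that only one of the three readings works, and it works by rounding: no whole number of losses in an arm of 24 lies between 16.7% and 20.8%. Section 9.1 does not say whether the 20% is per arm or overall, or a ceiling or a rate. Saying that 24 keeps 20 evaluable if no more than 4 per arm are lost would be true on every reading, and would cost only a sentence. CAP is the stated basis for the sample size, so its arithmetic deserves to be exact. Naming the test would also let a reader see that the rank-sum analysis has slightly under 90% power if CAP is normal.

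The arithmetic in this argument stands: 25 is the right answer for an expected 20% rate, and section 9.1 is silent on the test. What does not follow is a defect. The sentence is about the number in each arm and gives an upper limit, so the per-arm ceiling is its natural sense. A limit of 4 in 24 is the same whole-participant limit that the plan already states as up to 20%. The test is a missing detail that a reader can recover, because section 9.6 supplies the sidedness, the level and the planned test, and a t-test returns the stated figures.

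Discontinuation is also not the same as a missing CAP value. Replacement of non-starters, continued evaluation after an adverse-event stop, and the early-discontinuation scan all reduce the loss. They are a partial answer only. The early scan is reserved for those with at least 12 weeks on drug and is not a week-48 value. Section 6.4 also takes participants off study after 14 or more days without drug.

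**Conclusion.** The concern does not hold as a fault in the plan. Read per arm in whole participants, up to 20% of 24 is at most 4, and 20 remain, as section 9.1 says. Under the other two readings the gap is about one participant per arm, or one in total. It costs at most about 1.5 points of t-test power (90.2% to 88.7%), or raises the difference detectable with 90% power from 55.8 to 57.3 dB/m. These figures assume an SD of 53, equal allocation and a two-sided 0.05 test. The unnamed test is a gap that any analyst would fill from section 9.6 and the numbers themselves. Using ranks in place of a t-test costs under 2 points at 20 per arm if CAP is normal.

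Differences of this size are well inside the uncertainty of an SD borrowed from another population, for a secondary endpoint in an exploratory pilot. Neither rewording the allowance nor naming the test would alter enrolment, visits, the analysis or any conclusion, so no change is called for.
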